### **7.3 PATIENT SETS ANALYSED**

➤ **Screened Set:**

Screened set includes all patients who signed the ICF.

➤ **Entered Set:**

Entered set includes patients in screened set who met the eligibility criteria.

➤ **Treated Set:**

Patients in entered set who have received the study drug Praxbind™.

Analysis for all primary and secondary outcomes will be done on treated analysis set.

The following table defines the patient set is to be used for planned analysis.

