**Table 6.2: 1 Important Protocol Violation**

Category/ code	Description	Requirements	Detected by	Excluded From;
A	Entrance Criteria Not Met			
A1	Not met criteria for Treatment with Pradaxa and Praxbind™.			
A1.1	Patients not treated with Pradaxa (dabigatran etexilate) capsules or Patients treated with Pradaxa with no requirement of rapid reversal of the anticoagulant effects of dabigatran: 

• For emergency surgery/urgent procedures (or)

• In life-threatening or

	Patients did not receive Pradaxa or patients who received Pradaxa but not required Praxbind™ for reversal of anticoagulant effects of Pradaxa.	Programmatically	None

Category/ code	Description	Requirements	Detected by	Excluded From;
	uncontrolled bleeding			
A2	Inform consent			
A2.1	Written informed consent in accordance with International Conference on Harmonization Good Clinical Practice (GCP) guidelines and local legislation and/or regulations not obtained.	Informed consent not obtained.	Programmatically	None
B	Exclusion criteria met.			
B1	Participation in Other Clinical Trial			
B1.1	Participation in a Praxbind clinical trial.	Patient currently participating or participated previously in other Praxbind clinical trial	Manually	None

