**Table 6.3: 1 Patient sets analysed**

Class of outcomes	Patient set		
	Screened Set	Entered Set	Treated Set
Primary and key secondary outcomes (Safety)	-	-	X
(Other) Secondary and further outcomes	-	-	X
Demographic/baseline outcomes	-	X	-

Note: No other secondary and further endpoints mentioned in CTP.

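### SAP 7.3 restricts the primary safety population to eligible patients, while Table 6.2:1 excludes eligibility violators from nothing and 8.8 takes anyone dosed

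*SAP*

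**What the plan says.** SAP 7.3 defines three nested sets. "Screened set includes all patients who signed the ICF". "Entered set includes patients in screened set who met the eligibility criteria". The Treated Set is then "Patients in entered set who have received the study drug Praxbind™". The section continues: "Analysis for all primary and secondary outcomes will be done on treated analysis set". Table 6.3:1 repeats this, assigning the row that begins "Primary and key secondary outcomes (Safety" to the Treated Set and the row "Demographic/baseline outcomes" to the Entered Set.

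Table 6.2:1, in SAP 7.2, lists the important protocol violations. A1.1 is failure of the main inclusion criterion: "Patients did not receive Pradaxa or patients who received Pradaxa but not required Praxbind™". B1.1 is the exclusion criterion: "Patient currently participating or participated previously in other Praxbind clinical trial". A2.1 is absence of informed consent. For all three, the *Excluded From* column reads None. SAP 7.2 adds that there will be no per-protocol analysis and that the table is kept for completeness and as evidence of adherence. How affected data are handled is left to an agreement before database lock.

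SAP 8.8 takes patients with at least one dose of Praxbind into the safety analysis. It names no analysis set and states no eligibility condition.

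**The concern.** The primary outcome is a safety outcome: suspected ADRs and fatal AEs within 7 days of administration. Under 7.3 as written, eligibility acts as a filter on that outcome. A dosed patient who turns out to fail inclusion criterion 1, or to have taken part in a Praxbind trial, is not in the Entered Set. That patient is therefore not in the Treated Set or in the primary result. Table 6.2:1 says the same patient is excluded from nothing. Both statements cannot hold, and a programmer following the SAP has no rule for choosing between them.

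The protocol frames these events by exposure. Section 12.2 collects fatal AEs in anyone exposed to Praxbind, and the adverse-reaction definition in 12.1 covers use outside the marketing authorization. What is at stake is an ADR or death that is collected as the protocol requires and then missing from the numerator, with its patient missing from the denominator, of the primary summary.

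The case is foreseeable. The indication field in Protocol 10.2 and SAP 6.4 includes scheduled or planned procedures and an open *other* category, neither of which is in inclusion criterion 1.

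**Working it through.** The documents give no figure to reproduce: the study is descriptive, with no hypothesis and no derived sample size. The check is a comparison of the rules, followed by an illustration of size.

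**Step 1. The rules side by side.** Write C for consent signed, E for eligibility met and D for dosed. By SAP 7.3:

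- Screened = C
- Entered = C and E
- Treated = C and E and D

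Consider a consented, dosed patient with violation A1.1 or B1.1 (C and D hold, E does not):

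| Rule | Primary outcome | AE summary tables (8.8) |
|---|---|---|
| 7.3 literal, 8.8 read as a separate population | out | in |
| 7.3 literal, 8.8 read as a loose description of the Treated Set | out | out |
| Table 6.2:1, excluded from None | in | in |

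The safety label on the outcome row of Table 6.3:1 could support the second reading of 8.8. Under both readings, 7.3 contradicts the None entries.

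**Step 2. Effect on the primary outcome.** Inputs: 25 dosed patients (the cap in Protocol 10.4) and k dosed but ineligible patients. The value of k is an assumption, as the documents give no violation rate. The denominator is 25 for all dosed and 25 − k under 7.3. Intervals are exact (Clopper-Pearson) 95%: lower = Beta(0.025; x, n − x + 1), upper = Beta(0.975; x + 1, n − x). When x = 0 the lower limit is 0 and the upper is 1 − 0.025^(1/n); for n = 24 this is 1 − 0.025^(1/24) = 14.2%.

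With k = 1:

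| Where the events fall | Under 7.3 | All dosed |
|---|---|---|
| Only event is in the ineligible patient | 0/24 = 0% (0 to 14.2) | 1/25 = 4.0% (0.1 to 20.4) |
| One in an eligible patient, one in the ineligible patient | 1/24 = 4.2% (0.1 to 21.1) | 2/25 = 8.0% (1.0 to 26.0) |
| One in an eligible patient, none in the ineligible patient | 1/24 = 4.2% (0.1 to 21.1) | 1/25 = 4.0% (0.1 to 20.4) |

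Only the first row moves the result from zero to non-zero, and the third is negligible. If the single event is in an ineligible patient and k is 3 or 5, 7.3 gives 0/22 (upper limit 15.4%) or 0/20 (16.8%), still against 1/25.

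**Step 3. Effect on the secondary outcome.** This is the percentage treated for either labelled indication. If the k ineligible patients are those with another indication, the combined percentage among all dosed is (25 − k)/25: 96%, 88% and 80% for k = 1, 3 and 5. Under 7.3 it is (25 − k)/(25 − k) = 100% by construction, because the set admits only patients with one of those indications. The split between the two indications remains informative either way.

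**Step 4. Consent (A2.1).** Every set in 7.3 requires a signed ICF, so a patient without consent belongs to none of them. Table 6.2:1 nevertheless reads None, and 8.8 states no consent condition. This is a smaller, separate inconsistency.

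**The case against.** The best defence turns on the word *met*. If it means judged eligible at entry, a patient whose violation surfaces later stays in the Entered and Treated Sets, and the None entries for A1.1 and B1.1 are consistent with 7.3. The rest of 7.2 fits that reading: there is no per-protocol analysis, and violations are found programmatically or on review, that is, in data already collected. This is plausible and may be what was intended, but the SAP does not say it, and the literal wording says otherwise.

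Second, the protocol does not point only one way. Sections 10.1 and 10.1.2 describe the target as patients prescribed Praxbind under the approved label, while the abstract also speaks of all patients receiving it as prescribed by their physician. Sections 12.1 and 12.2 govern definitions and collection, not analysis sets. That is fair: they support an exposure-based set but do not prescribe one. The stronger support is in the SAP itself, in 8.8 and in the rejection of a per-protocol analysis.

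Third, the pre-lock deviation strategy could settle the matter. It states no rule, however, and in a single-arm study with no blinding, membership of the primary safety set would then be decided with the events in view.

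Fourth, the harm is limited. SAP 8 lists all study data by patient, 8.8.1 separately identifies deaths and other SAEs, and Protocol 12.2 sends serious ADRs and fatal AEs to the sponsor within 24 hours. This stands: no event would be hidden. The damage is confined to the summary numerator and denominator.

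**Conclusion.** The concern holds. SAP 7.3 and Table 6.2:1 give opposite answers for a dosed patient found ineligible, and 8.8 does not resolve the conflict. Followed literally, 7.3 removes that patient's ADR or death from the primary safety result.

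The textual conflict is certain; its numerical effect is conditional. There is none unless at least one dosed patient is ineligible. With one such patient among an assumed 25, the primary percentage changes by about 4 percentage points when that patient has an event and hardly at all otherwise. Because this is the population for the primary outcome and the correction costs almost nothing, it should be fixed before database lock.

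**What to change.** - **SAP 7.3:** define the Treated Set as all consented patients who received any Praxbind, regardless of the other eligibility criteria.
- **SAP 8.8:** name that set as the population for the primary, secondary and AE summary tables.
- **Table 6.3:1:** use the same set for the demographic and baseline row. The Treated Set would no longer sit inside the Entered Set, and baseline and outcome tables should describe the same patients.
- **Table 6.2:1:** keep it descriptive, with None for A1.1 and B1.1. State which sets, if any, an A2.1 patient belongs to.

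The secondary outcome moves to all consented dosed patients as well, so use for other indications would show in the percentage.

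The cost is a few sentences in 7.3, Table 6.3:1 and 8.8, plus a note on A2.1. No protocol change, extra data or extra tables are needed.

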**Table 6.3: 1 Patient sets analysed**

Class of outcomes	Patient set		
	Screened Set	Entered Set	Treated Set
Primary and key secondary outcomes (Safety)	-	-	X
(Other) Secondary and further outcomes	-	-	X
Demographic/baseline outcomes	-	X	-

Note: No other secondary and further endpoints mentioned in CTP.

### **7.5 POOLING OF CENTRES**

This section is not applicable because this is drug administration surveillance and no statistical model is involved in the analysis.

## **7.6 HANDLING OF MISSING DATA AND OUTLIERS**

No missing data analysis is planned for this study. Missing values will be considered as missing, no imputation will be done for the analysis purpose.

Missing or incomplete AE dates are imputed according to BI standards  (i.e. “Handling of missing and incomplete AE dates”).

## **7.7 BASELINE, TIME WINDOWS AND CALCULATED VISITS**

Data will be collected for patients who have been treated with Praxbind within 2 years. No formal visits are planned for this surveillance also there is no protocol mandated follow-up visits or procedures associated with the program.

Last non missing values observed prior to receiving the PraxbindTM will be considered as Baseline value.

## **8 PLANNED ANALYSIS**

The general principles listed below will be applied throughout the study:

- All study data will be included in individual patient study data listings. All summary tables will present descriptive statistics for the parameters being analyzed, wherever applicable.
- If the non-formatted data that are received (e.g., from the clinical database) are inconsistently presented, a decision on how to present the final data will be made on a case-by-case basis.
- When rounding is required, numbers 4 or below will be rounded down and number 5 or above will be rounded up.
- Numeric presentations:
  - Descriptive analysis for continuous data will include number of non-missing observations (n), mean, Standard deviation(SD), median, minimum, maximum,Q1, and Q3. Means, medians, Q1 and Q3 will be rounded to 1 decimal place more than the actual data. Minimum and maximum will be displayed with the same decimal precision as the original data.Q1 and Q3 will be presented with 1 decimal.
  - For categorical data, frequency(N) and percentage(%) will be presented. Percentages will be rounded to 1 decimal place. Percentages equal to 100 will be output as '100.0%'.
- All the data analysis will be done using SAS® version 9.2 or higher.
- Baseline assessments are the assessments taken prior to the administration of Praxbind for all patients. If there are multiple assessments collected on the same scheduled time, the average of these assessments will be used.
- The change from baseline is defined as the post-baseline value minus the baseline value.
- Missing data will not be imputed but will be analyzed as missing. Missing values will be represented with blank spaces. In cases where a value is missing due to non-evaluable then it will be represented with a hyphen “-”.

- If data summary is planned during the conduct of the trial and no data are generated satisfying the criteria then no data table will be generated with just a comment.

## **8.1 DEMOGRAPHIC AND OTHER BASELINE CHARACTERISTICS**

Patient demographic data at baseline visit(age, gender, weight, height, pregnancy status, Systolic blood pressure, Diastolic blood pressure, Pulse rate) will be summarized using descriptive statistics, frequency count and percentage

All the continuous data (age, weight, height, systolic blood pressure, diastolic blood pressure, and pulse rate) will be summarized using descriptive statistics (number of non-missing observations, mean, standard deviation, median, minimum, maximum, Q1 and Q3). Whereas all the categorical data (sex, pregnancy status) will be summarized using frequency counts and percentages.

In addition to the summary tables, listings will be provided by patients for all demographics and baseline characteristics data.

## **8.2 CONCOMITANT DISEASES AND MEDICATION**

Relevant past or present medical history will be listed individually by patient.

Medications used before the first dose will be considered as prior medications and medications started after the first dose in the study or medication used during the study will be recorded as concomitant medications.

Concomitant medications will be coded using the World Health Organization Drug Dictionary (WHO DD), Version June 2017 or later, and will be summarized using frequency counts and percentages as per ATC level 3 text.

## **8.3 TREATMENT COMPLIANCE**

No analysis planned for compliance of treatment.

## **8.4 PRIMARY OUTCOME(S)**

Any suspected ADRs and fatal AEs; with special focus on hypersensitivity and thrombotic event, occurred within 7 days after Praxbind™ administration will be analysed for primary outcome results.

## **8.5 SECONDARY OUTCOME (S)**

### **8.5.1 Secondary outcome(s)**

Percentage of patients who either received Praxbind™ for emergency surgery/urgent procedures or in life-threatening or uncontrolled bleeding at the end of 2 years will be analysed for secondary outcome results.

Frequency table for emergency surgery/urgent procedures or in life-threatening or uncontrolled bleeding will be generated to analyse.

### **8.5.2 (Other) Secondary outcome(s)**

This section is not applicable as no other secondary endpoint has been specified in the protocol.

## **8.7 EXTENT OF EXPOSURE**

This section is not applicable.

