10.2.2.2 Secondary outcomes

Percentage of patients who either received PraxbindTM for emergency surgery/urgent procedures or in life-threatening or uncontrolled bleeding at the end of 2 years.

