#### **➤ Site characteristics:**

To evaluate the diversity of sites the following information will be collected for each participating site:

- Multi-specialty hospitals with emergency management facilities and having access to Praxbind™
- Practice type (academic, non-academic, private, Government)
- Availability of prescription/medical records at the site.

➤ **Patient Data:**

- Year of Birth
- Gender: Male or Female
- Vital Signs
- Physical Examination
- Laboratory data (Data would be collected of lab results performed as a routine practice.  
No additional lab tests should be performed specifically for this study purpose)
- Pregnancy status in case of female patient

➤ **Medical History:**

- Name, dose and last intake of previous anticoagulant medications (Dabigatran);
- Pertaining to haemorrhagic risk factors or impact on safety outcomes (e.g. renal impairment, congenital or acquired coagulation disorders, thrombocytopenia or functional platelet defects, recent biopsy, recent surgery, major trauma, bacterial endocarditis, esophagitis, gastritis, gastroesophageal reflux, hepatic disorders, vascular disorders, neoplasms/cancer, inherited vascular disorder (aneurysms, arteriovenous malformation, microangiopathy) and the HAS-BLED score).
- Concomitant treatment pertaining to haemorrhagic risk factors or impact on safety outcomes (e.g. acetylsalicylic acid, non-steroidal anti-inflammatory drugs, clopidogrel, selective serotonin reuptake inhibitors or serotonin-norepinephrine reuptake inhibitors, Strong P-Gp inhibitors (e.g. Ketoconazol, Clarithromycin, ticagrelor), chemotherapy, radiation therapy).

➤ **Praxbind™ utilization:**

- Department (emergency, operating room, ICU, other patient setting);
- Type of surgery /procedure if applicable;
- Information on bleeding event including location (Gastrointestinal tract; Intracranial; Skin, Urogenital tract, Intramuscular, Retroperitoneal, Undefined location, otherdefined location) if applicable, and if bleeding was life-threatening (yes/no);

- Indication: life-threatening or uncontrolled bleeding requiring urgent medical intervention, emergency surgery or other urgent medical procedure necessitating rapid reversal of the anticoagulant effect of dabigatran prior to surgery/procedure, scheduled or planned surgery/procedure, other.

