- Dosage and administration (total dose administered and time interval between the administration of the two vials; vials to be taken one after the other, immediate administration of the second vial is mandatory);
- Premature PraxbindTM administration discontinuation (yes/no).
- In case if the patient requires an additional 5 g dose for the following conditions as per the label:
  - i. recurrence of clinically relevant bleeding together with prolonged clotting times, or
  - ii. if potential re-bleeding would be life-threatening and prolonged clotting times are observed, or
  - iii. patients require a second emergency surgery/urgent procedure and have prolonged clotting times.
- Information on restart of anticoagulation therapy (which anticoagulation treatment including dose and when was it restarted).
- All adverse drug reactions (ADRs, serious and non-serious) associated with PraxbindTM.
- All AEs with fatal outcome in patients exposed to PraxbindTM.

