### **7.2 IMPORTANT PROTOCOL VIOLATIONS**

This surveillance is mainly focused on prescription patterns of use of Praxbind in a clinical practice setting, with special focus on ADRs and fatal AEs. So in this surveillance per protocol (PP) analysis will not be considered. Hence, the iPV table will be included for completeness and also to demonstrate a level of quality (or adherence to the protocol).

The following table defines, but is not limited to, the different categories of important PVs:

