### **8.8.5 Others**

This section is not applicable as no other analysis is needed.

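### SAP 8 names a summary for one of eight drug-use items although the protocol commits every variable to descriptive statistics, and the SAP disagrees with itself on which treated patients are counted

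*SAP*

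**What the plan says.** **Objective and commitment.** Protocol 9 gives one main objective, the pattern of prescribing in routine practice, with special attention to ADRs and fatal AEs. SAP 7.2 repeats it: "This surveillance is mainly focused on prescription patterns of use of Praxbind in a clinical practice setting". Protocol 10.6.1 promises descriptive statistics for all variables, including 95% CIs where they suit the variable. SAP 4 says it is built on protocol 10.6, and SAP 5 reports no change.

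**What is recorded.** SAP 6.4 lists ten bullets under Praxbind utilisation. Two are ADRs and fatal AEs; the other eight concern prescribing and use. One of them reads "Dosage and administration (total dose administered and time interval between the administration of the two vials". The indication bullet has four categories, the last two being "scheduled or planned surgery/procedure, other".

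**What is analysed.** SAP 8.7 (extent of exposure) says "This section is not applicable". SAP 8.3 says "No analysis planned for compliance of treatment". SAP 8.5.1 says "Frequency table for emergency surgery/urgent procedures or in life-threatening or uncontrolled bleeding will be generated to analyse", which serves the secondary outcome in protocol 10.2.2.2: "Percentage of patients who either received PraxbindTM for emergency surgery/urgent procedures or in life-threatening or uncontrolled bleeding at the end of 2 years". The general rules in SAP 8 put all data into patient listings, set formats for continuous and categorical summaries, and list no confidence interval.

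**Who is analysed.** SAP 7.3 builds the Treated Set from patients who met the eligibility criteria and analyses both formal outcomes on it. SAP Table 6.2:1 enters None under exclusions for every listed violation, including failure to meet the treatment criteria. SAP 8.8 takes anyone who had at least one dose.

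**The concern.** In a descriptive study the planned summaries are the analysis. If prescribing is the main objective, the SAP should say how each prescribing item will be summarised. Instead, the section where dose, vial interval, early discontinuation and additional dosing would naturally be described is marked as not applicable, and the department, procedure, bleeding and restart items have no section at all. Where a SAP promises no change from the protocol but its own entries point the other way, two analysts could produce different reports and both claim to have followed the plan.

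The denominator is also at stake. Use outside the two labelled indications is one of the things a prescribing survey can show. The indication variable has categories for it, but the analysis set as defined removes those patients.

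**Working it through.** The plan has no figure to reproduce: the cap of 25 patients in protocol 10.4 is not derived from a formula. The check is a match of items to analyses, followed by two short calculations.

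**Step 1. Match each SAP 6.4 use item to the summaries named in SAP 8.1 to 8.8.** 10 bullets − 2 safety bullets = 8 items.

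| Item | Form fixed in SAP | Summary named in SAP 8 |
|---|---|---|
| Department | 4 settings | none |
| Procedure type | not coded | none |
| Bleeding site; life-threatening or not | 8 sites; yes/no | none |
| Indication | 4 categories | yes, 8.5.1, for two of the four |
| Total dose; vial interval | continuous | none |
| Premature discontinuation | yes/no | none for the item; 8.8.1 tabulates AEs causing discontinuation |
| Additional dose | 3 conditions | none |
| Anticoagulation restart | drug, dose, timing; no derivation | none for the item; 8.2 may show the drug at ATC level 3, without dose or timing |

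Named: 1. Not named: 8 − 1 = 7. Of the seven, three would fit under 8.7 (dose and interval, discontinuation, additional dose) and four have no section. Five of the seven already have fixed categories or fall under the general rule for continuous data. Two, procedure type and time to restart, still need a definition.

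**Step 2. The denominator.** Protocol 10.1.2 admits only the two labelled indications. Let E be the number of treated patients who met eligibility. Under SAP 7.3 the Treated Set has size E, and every member has one of those two indications. Then

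secondary percentage = E / E = 100%,

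and the planned-procedure and other categories are empty. With all treated patients as the denominator, as SAP 8.8 implies, the result can vary. For illustration, if 5 of 25 were treated for another reason, it would be (25 − 5)/25 = 80%. The split between the two labelled indications remains informative under either definition.

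**Step 3. What an interval would show.** Exact (Clopper-Pearson) 95% limits for x of n are the Beta quantiles B(0.025; x, n − x + 1) and B(0.975; x + 1, n − x), with lower limit 0 when x = 0. For 0/25 the upper limit is 1 − 0.025^(1/25) = 13.7%. The counts are illustrative.

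| x/n | 95% CI |
|---|---|
| 0/25 | 0 to 13.7% |
| 5/25 | 6.8 to 40.7% |
| 12/25 | 27.8 to 68.7% |

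These widths describe imprecision at the maximum sample size. They do not measure harm from a missing table.

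**The case against.** The strongest reply is that the summaries are already planned. Protocol 10.6.1 covers all variables, SAP 4 and 5 adopt it unchanged, and SAP 8 sets general formats. Much of this stands. A reader might infer that the seven items would appear as listings only, with no planned summary. The documents do not support that: the listing rule covers all data, including data that are also tabulated, and the protocol commitment carries over by reference. What remains is that SAP 8 itemises its tables for demographics, concomitant medication, AEs and laboratory data, does not do so here, and marks the nearest section as not applicable.

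A reader might also infer that most of the main objective goes unanalysed. That would weigh all bullets equally. The objective also stresses ADRs and fatal AEs, for which SAP 8.8.1 names ten tables, and the only formal use outcome, indication, has its table.

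SAP 8.8.5, "This section is not applicable as no other analysis is needed", is tempting as evidence, but it sits under safety and says nothing about drug use.

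It can be said that 8.7 merely follows protocol 10.2.1, which marks exposures as not applicable, and that only one standard dose is studied. But SAP 6.4 records delivered dose, interval, discontinuation and additional dosing, and SAP 8.8.1 plans tables of AEs causing discontinuation and dose reduction. The plan therefore allows for variation. The protocol's checklist also answers yes on exposure, citing 10.2 and 10.2.1.

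Three smaller points stand. The missing interval affects every SAP summary, not just these items. A four-category indication table on the Treated Set as now defined would leave two rows empty. And the public SAP skips sections 6.3, 7.4, 8.6 and 10, so removed text cannot be ruled out. The contents list puts every entry from 8.4 to 8.8 on page 17, which leaves under a page for any 8.6. Page 23, between sections 9 and 11, is unaccounted for.

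**Conclusion.** The point holds as a conflict between the SAP's entries and the protocol's commitment. A summary is named for 1 of 8 use items and for none of the other 7; 8.7 and 8.3 decline the analyses nearest to three of those; and the protocol's 95% CIs are absent from the SAP's statistics. It is not established that the seven items would go unsummarised.

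The consequence is limited. There are at most 25 patients and no hypothesis test, both formal outcomes have planned analyses, and simple proportions could be counted by hand. After-the-fact choice is a concern for only two items, procedure-type coding and time to restart.

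The denominator conflict is separate and concerns the secondary outcome directly: SAP 7.3, Table 6.2:1 and 8.8 cannot all be applied as written if an ineligible patient is treated. If none is, they agree. The 100% result assumes the literal reading of SAP 7.3.

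All of this rests on the public text of the SAP.

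**What to change.** - In SAP 8.7, or a new utilisation subsection, replace the not-applicable entry with tables of n/N and %, with exact 95% CI where appropriate, for department, procedure type, bleeding site and life-threatening status, premature discontinuation, additional dose by recorded reason, and anticoagulation restart.
- Summarise recorded total dose, vial interval and time to restart descriptively.
- Add the 95% CI to the statistics listed in SAP 8, in line with protocol 10.6.1.
- Define the coding of procedure type and the derivation of time to restart before database lock.
- Reconcile SAP 7.3, Table 6.2:1 and 8.8 so that all patients who received the drug are in one stated denominator. Tabulate all four indication categories on it, and keep the 8.5.1 table as the secondary outcome.

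The cost is SAP text and two or three extra tables. No new data are needed.
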